لذلك الادوية من مجموعة الستاتين و هي ادوية تقلل الكوليستيرول في الدم و وجد ان لها تأثيرا إيجابيا في علاج مكان الخلع لما وجد لها من عدة فوائد مثل مضادة لالتهاب و مضادة للأكسدة و زيادة البروتينات العظمية المتعددة عن طريق تحفيز الخلايا الام على التحول لخلايا بناء العظم و تساعد على التكلىس و لها تأثير يقلل نشاط الخلايا الأكلة للعظم.

البلازما الغنية بعوامل النمو باستخدام كلوريد الكالسيوم تكون هيكل من ألياف الفيبرين الذي شاع استخدامه كمساعد لتجديد الأنسجة و يقلل المضاعفات مثل الالتهاب و الألم.

بالرغم من الدراسات المتعددة عن أهمية كل من أدوية الستاتين ، او هيكل الفيبرين المشتق من البلازما الغنية بعوامل النمو منفصليين ، لا توجد دراسات كافية عن تأثيره محمل على هيكل الفيبرين و لهذا تهدف هذه الدراسة لمقارنة النتائج بعد استخدام دواء الاتورفاستاتين المحمل على هيكل الفيبرين المشتق من البلازما الغنية بعوامل

النمو، و دواء الاتورفاستاتين المحمول على جل الميثيل سيليلوز و مقارنتهم بعدم وضع اي شيء مكان الخلع و ذلك عن طريق القياسات الفعلية لطول و عرض العظم قبل الخلع و بعد الخلع و عن طريق تحليل عينة العظم المأخوذة بعد الخلع بثمان أسابيع أثناء عملية زراعة السن الجديدة .

المرضى و الطرق:

سيتم إجراء الدراسة الحالية على مجموع ٣٠ شخص من الجنسين على ان يكون لديهم اسنان ليس لها علاج الا الخلع و سيتم تقسيم هذه المواقع عشوائيا إلى ٣ مجموعات. والمجموعة الاولى ستضم ١٠ موقع بعد الخلع يتم ملئها بدواء الاتورفاستاتين المحمول على البلازما الغنية بعوامل النمو والمجموعة الثانية ستضم ١٠ موقع بعد الخلع يتم ملئها بدواء الاتورفاستاتين المحمول على جل الميثيل سيليلوز و المجموعة الثالثة ستضم ١٠ موقع
سيتم الخلع بدون ملء مكان بعد الخلع ب اي شيء .

سيتم عمل قياسات اكلينيكية لارتفاع و عرض العظم مكان الخلع قبل العلاجات و بعد ٨ اسابيع كما سيتم أخذ عينات من العظم المتكون بعد ثمان أسابيع بعد عملية الخلع و تحليلها هستولوجيا تحت الميكروскоп و سيتم تعويض السن المخلوعة عن طريق عملية زراعة سن بديلة في نفس الزيارة بعد أخذ العينة .

سيتم جمع النتائج و تحليلها احصائيا

Statistical Analysis plan

The collected data was tabulated and analyzed using Statistical Package for Social Science (***SPSS 15.0 for windows; SPSS Inc, Chicago, IL, 2001***). First; the normality of distribution of parameters was evaluated by **One-Sample Kolmogrovo-smirnov test**. Data were expressed as **mean and standard deviation (SD)**. **One-Way ANOVA test was used** for comparison between more than two study group means. Pairwise multiple comparisons to test the difference between each pair of means was performed using **Tukey HSD test**, and yield a matrix where different asterisks indicate significantly different group means. **Paired t test** was used to compare changes within same group. For all tests, **P <0.05 was considered significant**.

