- 2) Clinical measurements of dimensional changes after extraction.

Subjects and methods

Thirty patients will be selected from the outpatient clinic of Oral Medicine, Periodontology, and Oral Diagnosis department, Faculty of Dentistry, Ain Shams University

Inclusions criteria:

1. Healthy adult patients as evidenced by Burkett's oral medicine health history questionnaire.
2. Both sexes.
3. Age from 20 –50 years old.
4. Having at least one hopeless tooth indicated for extraction.
5. Patient should agree to sign a written consent after the nature of the study will be explained.

Exclusion criteria:

1. Smokers.
2. Pregnant and breast feeding females.
3. Prisoners and handicapped patients.

Patients met the eligibility criteria will be randomly allocated using sequentially numbered sealed envelopes into 3 treatment modalities groups:-

Group I (PRGF/ATV): Will include 10 patients undergoing single tooth extraction followed by socket fill with PRGF loaded with Atorvastatin then suturing the socket.

Group II (ATV): Will include 10 patients undergoing single tooth extraction followed by socket fill with Atrovastatin gel then suturing the socket.

Group IIIEmpty socket(control) : Will include 10 patients undergoing single tooth extraction then suturing the socket.

All patients will receive implants after taking the bone biopsy after 8 weeks for histomorphometric analysis.

This proposal will be reviewed by the research ethics committee, the procedure will be fully explained to the patients and they will sign an informed consent.

Surgical procedure and clinical measurements:

- 1- Patients will undergo atraumatic extraction under local anesthesia for the involved tooth, to preserve bone and soft tissue followed by socket curettage.
- 2- Prior to surgery baseline clinical measurements (bone height measured by periodontal probe and bone width by bone caliper) will be taken for the alveolar ridge.
- 3- Socket will be filled with one of the assigned augmentation modalities;

Preparation of PRGF/ATV :

9ml venous blood will be collected from the same patient from peripheral circulation. The blood will be deposited in 3.8% w/v sodium citrate 1:9v/v. Platelet-rich in growth factors will be separated by centrifugation at 580 g for 8 minutes at room temperature. After centrifugation blood will be separated into plasma and cells, fractionation of plasma into 3 fractions:

Platelet very rich in growth factors - F3

Plasma with growth factors -F2

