Plasma poor with growth factors - F1

To produce the (PRGF)(F3) loaded with Atorvastatin we will obtain by carefully pipeting a 1ml fraction of plasma immediately above the red blood then mixed with a weighted amount of Atrovastatin powder to produce 1.2% (PRGF /ATV) formulation, then 10% calcium chloride (50 µL for each 1 ml plasma) will be added and incubated

for 20 minutes in 37 c to produce a semi-solid mass (*Anitua E, 2001*).

Preparation of 1.2% (ATV) gel:

Atrovastatin methylcellulose gel will be prepared, by adding the required amount of biocompatible solvent to an accurately weighed amount of methylcellulose heated to obtain a clear solution then a weighed amount of ATV will be added to the above

solution and dissolved completely to obtain a homogeneous phase of polymer with a concentration 1.2% as described by *Pradeep AR, et al. 2013*.

4- Socket will be sutured.

5-Postoperative medications will include (Amoxicillin 500 mg t.d.s, Flagyl 500 mg twice/day and antiseptic mouth wash for 1 week).

6- Post operative instruction will be given to the patient and Suture will be removed after 1-2 weeks post operatively

7- Patient will be instructed to avoid wearing any prosthetic restoration.

8-After 8 weeks patient will come for postoperative clinical measurements and for taking biopsy and implant placement.

Histological Examination :-

Bone Biopsy will be taken by a trephine bur and the implant will be inserted in the same visit , and correspond to a type 2 delay according to the International Team for Implantology classification (*Chen ST & Buser D.2008*).

10- All the biopsy specimens will be fixed in 10% buffered formalin and demineralized in 10% ethylenediamine tetra acidic acid solution. A 7- μm -thick longitudinal section, representing the central part of each core specimen, will be stained with hematoxylin and eosin (H&E) for histologic examination. The histologic section will be examined using a research light microscope, and photomicrographs will be taken with the attached digital camera.

11- Histomorphometric measurement of the tissue image will be performed using the image analysis software.

- Total area of newly regenerated tissue including the newly formed bone above the old basal bone within the obtained core and the adjacent soft tissue .

Statistical analysis:

All the clinical and histomorphometric data will be collected, tabulated and subjected to statistical analysis.

References

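### Does the unspecified Kolmogorov-Smirnov normality check undermine the ANOVA and paired t tests?

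*SAP*

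**What the plan says.** The SAP is one paragraph in the past tense. On normality it says that "the normality of distribution of parameters was evaluated by" a "One-Sample Kolmogrovo-smirnov test", and nothing further. Data are summarised by mean and SD. One-way ANOVA is used "for comparison between more than two study group means", followed by Tukey HSD for pairs, and a paired t test "was used to compare changes within same group". The level is 0.05 throughout. None of these analyses depends on the normality result, and no transformation or rank-based alternative is named.

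The Protocol adds no method. Its Statistical analysis section says "All the clinical and histomorphometric data will be collected, tabulated and subjected to statistical analysis". Its Subjects and methods section sets three groups of 10, 30 patients in all. The clinical outcomes are "bone height measured by periodontal probe and bone width by bone caliper", taken before surgery and at 8 weeks. The biopsy for histomorphometry is taken once, at 8 weeks.

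**The concern.** A standard one-sample Kolmogorov-Smirnov test assumes that the reference mean and SD are known in advance. If they are estimated from the same sample and the usual critical values are kept, the test becomes extremely conservative. The Lilliefors correction deals with this, but the SAP does not say whether it is applied. The unit of testing is also open, and it matters: 10 values per group give far less sensitivity than 30 pooled.

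The check comes before the parametric tests in the SAP, so a reader could take a non-significant result as support for them. Under the uncorrected reading that support would be empty. The within-group paired t test, with only 10 differences, has least protection from sample size, so skew there could distort its error rate unnoticed.

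**Working it through.** **Inputs.** Groups of 10 and a total of 30 come from the Protocol, Subjects and methods. The 0.05 level and the tests come from the SAP. Neither document gives an outcome distribution, an SD or a performance figure for the normality test, so there is no plan figure to reproduce. The distributions below are assumptions.

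**1. Critical values.** The statistic is D = max |Fn(x) − Φ((x − mean)/SD)|, with mean and SD taken from the sample.
- Uncorrected, asymptotic: 1.358/√10 = 0.429 and 1.358/√30 = 0.248.
- Uncorrected, exact: 0.409 (n = 10) and 0.242 (n = 30).
- Correct 5% values when mean and SD are estimated (simulated): 0.262 and 0.159.

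**2. How often non-normality is flagged.** Each case used 100,000 samples (10,000 for Shapiro-Wilk). Uncorrected ranges span the asymptotic and exact critical values.

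| Shape | n=10 uncorrected | n=10 Lilliefors | n=10 Shapiro-Wilk | n=30 uncorrected | n=30 Lilliefors |
|---|---|---|---|---|---|
| Normal | 0.001–0.002% | 5.1% | 5.0% | 0.007–0.012% | 5.0% |
| Lognormal, log-SD 0.5 | 0.05–0.15% | 18.2% | 23.9% | 2.8–3.7% | 48.5% |
| Exponential | 0.13–0.36% | 29.8% | 43.7% | 9.1–11.6% | 78.3% |
| Lognormal, log-SD 1 | 1.5–2.8% | 46.3% | 60.4% | 38.5–42.9% | 93.1% |

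The statistical point is therefore right: an uncorrected pass at n = 10 carries almost no information.

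**3. What depends on the result.** As the SAP is written, nothing does. ANOVA, Tukey and the paired t test are run whether the check passes or fails. A sharper test would leave their P values as they are.

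**4. ANOVA error rate.** With three groups of 10 of equal shape (normal, exponential, or lognormal with log-SD 0.3 to 1), ANOVA rejects a true null in 3.2 to 5.1% of trials.

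**5. ANOVA power under skew.** Two ways of placing a shift of 1.3 SDs in one arm:
- Multiplicative (1.3 log-SDs): 82, 79, 74 and 65% at log-SD 0.3, 0.5, 0.75 and 1, against 82% for normal data. This shift also multiplies the shifted arm's SD by exp(1.3 × log-SD), which at log-SD 1 is exp(1.3) ≈ 3.7.
- Additive (1.3 raw SDs, spreads equal): 82, 83, 84 and 86% at the same log-SDs.

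The loss in the first version comes with unequal spread; skew alone does not produce it.

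**6. Paired t test, n = 10.** Two nulls:
- The differences are themselves skewed with mean zero: 6.0% (log-SD 0.3), 8.1% (0.5), 9.7% (exponential) and 16.0% (log-SD 1).
- Baseline and 8-week values are skewed but exchangeable, so the differences are symmetric (within-patient log-scale correlation 0 or 0.7): 4.5–4.9%, 4.3–4.5% and 2.8–3.2% at log-SD 0.3, 0.5 and 1.

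The direction of the error depends on which null is assumed. Because histology is taken once, the paired test can apply only to height and width. A log-SD of 1 means a coefficient of variation of √(e − 1) ≈ 131%, and nothing in the documents suggests that for probe or caliper readings.

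**The case for a change.** The best case for a change is that the check cannot be interpreted as written. For log-SD 1, the readings that the text allows run from 1.5% detection (uncorrected, per group) to 93% (Lilliefors, pooled). Passing also gives no protection: among skewed samples that pass the uncorrected per-group test, the paired t test still rejects 6.0 to 16.5% under the skewed-difference null. Naming the version and unit, or dropping the test, would cost nothing.

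The first part stands. Version and unit are missing, and an uncorrected pass should not be offered as evidence of normality. But neither document reports such a pass or rests an analysis on one.

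The missing rule for what follows a rejection is not a defect either. A fixed analysis that no pretest can switch is good practice, and the SAP as written already has one. A better test would add little at this size: at n = 10 Shapiro-Wilk still misses about 40% of samples at log-SD 1 (100 − 60.4) and 76% at log-SD 0.5 (100 − 23.9).

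A permutation F test as a sensitivity analysis is a preference. At log-SD 0.3 and 0.5 its power is 82 and 80%, against 82 and 79% for ANOVA. It does not cure unequal spread: with equal means and different log-SDs it rejects 10.2 to 13.6%, against 9.6 to 13.0% for ANOVA.

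**Conclusion.** No change to the plan follows. The SAP leaves out detail about a descriptive check that selects no analysis. An analyst can fill that gap sensibly by inspecting the residuals and the paired differences, without touching the stated tests. The near-blindness of an uncorrected Kolmogorov-Smirnov test at n = 10 (at most 2.8% detection for the shapes in the table) is real, but it is conditional on the uncorrected version having been used, which the documents do not show. It limits how a non-significant result should be read; it does not make the ANOVA, Tukey or paired t results wrong. The figures that suggest harm, 6 to 16% for the paired t test and 65% power for ANOVA, each depend on a chosen scenario, and equally plausible alternatives give about 3 to 5% and 82 to 86%. All rest on assumed distributions.

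### Bone height and width: the SAP does not say whether the between-arm ANOVA compares change or 8-week values; ANCOVA on the baseline already collected would settle it at little cost

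*SAP*

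**What the plan says.** The protocol (Surgical procedure and clinical measurements, item 2) provides a baseline: "Prior to surgery baseline clinical measurements (bone height measured by periodontal probe and bone width by bone caliper) will be taken". Item 8 of the same section repeats the clinical measurements at 8 weeks. Each patient therefore has two values of height and two of width.

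The SAP's between-arm test is one-way ANOVA "for comparison between more than two study group means". It continues: "Pairwise multiple comparisons to test the difference between each pair of means was performed using" Tukey HSD. Change is mentioned only for the paired t test, which "was used to compare changes within same group". No covariate is named.

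The protocol's Statistical analysis section does not help: "All the clinical and histomorphometric data will be collected, tabulated and subjected to statistical analysis". The nearest thing to a definition is item 2 of the aim, "Clinical measurements of dimensional changes after extraction", together with the Arabic summary, which describes height and width before and after extraction. Both lean towards change, but neither is tied to the ANOVA.

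**The concern.** With a baseline and one follow-up value, a between-arm ANOVA can be run on the 8-week value or on the change. The two can reach different conclusions from the same data, and which is more powerful depends on the correlation between the two measurements. If the plan names neither, the choice can be made after the results are seen.

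Precision is also scarce. The three arms have 10 patients each (for example, "Group II (ATV): Will include 10 patients undergoing single tooth extraction"). The pre-surgery value is collected anyway, yet the between-arm test as written does not adjust for it.

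**Working it through.** **Inputs from the documents.** Three arms of 10; significance at P < 0.05; one-way ANOVA with Tukey HSD. The plan has no power figure to reproduce.

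**Assumptions.** The documents give no SDs, correlation or effect size. Take the baseline SD as 1, the 8-week SD as s = 0.8, 1.0 or 1.2, and the baseline-to-8-week correlation as r = 0, 0.3, 0.5, 0.7, 0.8 or 0.9. That makes 18 settings. Data are bivariate normal with a common slope, and one arm is shifted by 1 SD of the 8-week value (d = s).

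**Residual SD under each analysis.**
- 8-week value: s
- Change: √(1 + s² − 2rs)
- ANCOVA: s√(1 − r²)

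The change variance minus the ANCOVA variance is (1 − rs)², which is never negative. Change has a smaller SD than the 8-week value only when r > 1/(2s), which is r > 0.5 with equal SDs.

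**Critical values.** Tukey q/√2 is 2.479 on 27 df (ANOVA) and 2.485 on 26 df (ANCOVA).

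**Power for one pair.** This is noncentral t with noncentrality d / (SD × √(2/10)). For ANCOVA, √(2/10) becomes √(2/10 + D²/W), where D is the chance baseline difference between the two arms and W the within-arm baseline sum of squares; power is averaged over chance imbalance.

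Example, s = 1 and r = 0.7:
- 8-week: 1/(1 × 0.447) = 2.24, power 0.42.
- Change: SD = √0.6 = 0.775; 1/(0.775 × 0.447) = 2.89, power 0.66.
- ANCOVA: SD = √0.51 = 0.714; 1/(0.714 × 0.447) = 3.13 before the imbalance term, power 0.72 after it.

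Because the shift is one 8-week SD, the 8-week and ANCOVA columns do not depend on s.

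| r | 8-week ANOVA | Change, s = 0.8 | Change, s = 1.0 | Change, s = 1.2 | ANCOVA |
|---|---|---|---|---|---|
| 0 | 0.42 | 0.16 | 0.20 | 0.24 | 0.40 |
| 0.3 | 0.42 | 0.23 | 0.30 | 0.35 | 0.44 |
| 0.5 | 0.42 | 0.32 | 0.42 | 0.48 | 0.53 |
| 0.7 | 0.42 | 0.51 | 0.66 | 0.72 | 0.72 |
| 0.8 | 0.42 | 0.69 | 0.85 | 0.88 | 0.87 |
| 0.9 | 0.42 | 0.93 | 0.99 | 0.99 | 0.99 |

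ANCOVA's largest shortfalls are 0.02 against the 8-week ANOVA (r = 0) and 0.014 against change (s = 1.2, r = 0.8). In the second case rs = 0.96, so change has almost the ANCOVA residual SD and saves a degree of freedom.

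**Leaving the variable open.** Simulation, 100,000 trials per setting:
- No true difference: each analysis, fixed in advance, has family-wise error of 0.048 to 0.051. If a significant pair from either ANOVA may be reported, it is 0.082 (s = 1.2, r = 0) to 0.097 (s = 0.8, high r).
- True 1 SD difference: the two ANOVAs disagree on that pair in 25% (s = 1.2, r = 0) to 59% (s = 0.8, r = 0.9) of trials; 42% at r = 0.7 with equal SDs.

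**Why ANCOVA closes the choice.** If Y = α + τ(arm) + βX + e, then Y − X = α + τ(arm) + (β − 1)X + e. The arm effect, its standard error and its test are the same for either outcome.

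**The case against.** The strongest reply is that the documents, read together, already point to change: the aim and the Arabic summary both do, and nothing points to a comparison of 8-week values alone. On that view one sentence is missing, and naming change would close the gap completely. This stands. ANCOVA is the better choice, not the only valid one.

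The inflated error is also conditional. It arises only if both analyses are run and the favourable one is reported, and nothing in the documents suggests that intention. The disagreement rate partly restates the difference in power. Both points are fair: the figures measure the room the SAP leaves, not a fault in either test.

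The gain over change is not guaranteed. With equal SDs it is 0.02 at r = 0.8 and nil at r = 0.9; with s = 1.2 it is slightly negative from r = 0.7. ANCOVA also assumes linearity and a common slope, which are hard to check with 10 per arm. The 0.02 bound is for 10 analysed per arm; over a wider range of effect sizes, the worst shortfall for a Tukey pair is 0.021 with 10 per arm, 0.024 with 9 and 0.027 with 8. These are real limits, but the possible loss stays small beside the gains: 0.11 at r = 0.5 with equal SDs, and about 0.2 over change at r = 0.5 to 0.8 when s = 0.8.

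Finally, the SAP is written in the past tense. If the analysis has been done, the benefit of fixing the method in advance is gone, and the main request is to disclose which variable was compared.

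**Conclusion.** The concern holds. The SAP does not define the between-arm variable for bone height and width and makes no use of the baseline in that comparison. If either ANOVA may be reported, family-wise error per measurement is roughly 0.08 to 0.10. Neither ANOVA is a safe choice without knowing r: with equal SDs, change has 0.20 power against 0.42 at r = 0, while the 8-week value has 0.42 against 0.85 at r = 0.8. ANCOVA is best or within 0.02 of best in all 18 settings. Confidence is medium, because r, the SDs and the 1 SD effect are assumptions, and the results also rest on normal data, equal variances across arms and a common slope. The change is recommended rather than essential, since either ANOVA is valid once fixed.

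**What to change.** **Preferred.** For height and for width separately, specify ANCOVA of the 8-week value on arm (three levels) and the pre-surgery value of the same measurement. Report the three adjusted pairwise differences with Tukey-type adjusted P values and simultaneous 95% confidence intervals. If the software offers no Tukey adjustment with a covariate, compare |adjusted difference / SE| with 2.485; this cutoff is for 26 residual df with all 30 patients analysed and must be recomputed if any are lost.

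**Minimum.** If one-way ANOVA is kept, state in the SAP that it is run on change.

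Keep one-way ANOVA with Tukey HSD for histomorphometry, which has no baseline.

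**If the analysis has already been run.** State which variable was compared, and label any ANCOVA as added later.

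**Cost.** No new measurement; SAP wording if the analysis is still to come; one residual degree of freedom (27 to 26); the linearity and common-slope assumptions; and the power shortfalls given above. Bonferroni in place of Tukey (cutoff 2.559) would cost up to a further 0.03. It would leave ANCOVA 0.04 below the 8-week ANOVA at r = 0, and 0.029 below change at s = 1.2 with r = 0.7 (0.694 against 0.723) or r = 0.8 (0.855 against 0.884). The Tukey cutoff is therefore preferable.

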The degree of residual ridge resorption is closely related to the time since tooth extraction in both maxilla and mandible(*Ulm C, et al.1992*). The reduction in width is usually greater than the loss in height, and bone resorption is significantly larger at the buccal than at the lingual side (*Lekovic V, et al.1997*).

According to the Osteology Consensus Group 2011, ridge preservation is a general term for interventions that aim to preserve the ridge volume within the envelope existing at the time of extraction(*Christoph HF, et al 2011*).

In order to reduce alveolar bone dimensional changes, several techniques aiming at enhancing the regeneration process in the extraction socket have been adopted. Such as filling the socket with autogenous bone grafts or bone substitutes, guided bone regeneration (GBR) with resorbable or non-resorbable barriers and the use of various bone promoting molecules such as enamel matrix derivatives, recombinant growth and differentiation factors and autologous platelet concentrates (*Darby I, et al. 2009, Horowitz R, et al. 2012*).

Statins (hydroxymethylglutaryl co-enzyme A reductase inhibitors) are a group of lipid-lowering drugs that are widely used to prevent cardiovascular events (*Sotiriou CG & Cheng JW. 2000*), they are used orally to treat hypercholesterolaemia and hyperlipidaemia with well documented safety profile (*Guthrie RM, 2006*).

Furthermore, statins have been reported to stimulate the expression of bone anabolic factors, such as vascular endothelial growth factor and BMP-2 (*Maeda T, et al. 2003*), and to promote osteoblast differentiation and mineralization. In addition, it has been suggested that statins directly affect osteoclasts through mechanisms analogous to those of bisphosphonates (*Staal A, et al. 2003, Maeda T, et al. 2004*).

Statins can also modify the inflammatory cascades through pleiotropic actions at multiple levels, such as changing inflammatory mediators, altering leukocyte-endothelial cell interaction, and reducing expression of major histocompatibility complex- II (*Terblanche M, et al. 2007*).

Among statin drugs; Atrovastatin (ATV) has been demonstrated to exhibit favorable effects in the treatment of bone remodeling disorders and bone fractures through the promotion of osteogenesis and the reduction of bone resorption (*Wang JW, et al. 2007*).

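### For ridge height and width, the SAP does not say which test supports the treatment conclusion, and the only test it ties to change is a paired t test within each arm.

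*SAP*

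**What the plan says.** The SAP is one paragraph. It plans one-way ANOVA "for comparison between more than two study group means". It continues: "Pairwise multiple comparisons to test the difference between each pair of means was performed using" Tukey HSD. It then adds a paired t test, which "was used to compare changes within same group". One threshold covers every test: "P <0.05 was considered significant". The SAP does not say whether the group means in the ANOVA and Tukey tests are 8-week values or changes from baseline. It does not rank the tests or label any of them descriptive. The protocol's own Statistical analysis section names no test.

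Under Surgical procedure and clinical measurements, the protocol takes bone height and width before surgery and again at 8 weeks. There is no other postoperative measurement, and the biopsy is taken only at 8 weeks. The paired test can therefore only be the baseline-to-8-week change in height or width within an arm.

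The Aim of the study is comparative, and its second item reads "Clinical measurements of dimensional changes after extraction". On the natural course, the protocol's background says: "The degree of residual ridge resorption is closely related to the time since tooth extraction".

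**The concern.** The second aim compares arms on dimensional change, yet the one analysis that the SAP explicitly attaches to change makes no comparison between arms. The paired test asks whether an arm's ridge changed at all. In an untreated socket the protocol expects that it did. A significant loss in a treated arm may be no more than the natural course, and a non-significant loss in 10 sockets is weak evidence that bone was preserved. Only comparison with a concurrent arm removes the natural course.

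Because the SAP gives the paired test the same significance status as the between-arm tests, someone could follow it to the letter and report a significant loss in empty sockets beside a non-significant loss in a treated arm as ridge preservation. The opposite error is also possible: a treatment that truly reduces resorption could be reported as failing because its own arm still lost bone significantly.

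**Working it through.** **Inputs from the documents**
- Sample size: "Thirty patients will be selected from the outpatient clinic", 10 per arm in three arms (Protocol, Subjects and methods).
- Paired t test within arm, level 0.05 (SAP).
- Height and width measured before surgery and at 8 weeks only (Protocol).

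**Assumptions**
- Two-sided tests (the SAP does not state sidedness).
- Normal changes with equal SD, independent arms, complete data, one dimension considered at a time.
- d = true mean loss divided by the SD of the change, the same in all three arms, so that there is no treatment effect. The documents give no mean change or SD, so d is shown over a range.

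**Step 1: the plan's own figure.** There is no sample-size calculation to reproduce. The only stated figure is the 0.05 level. At d = 0, a two-sided paired t test with n = 10 (9 degrees of freedom) rejects in 5.0% of trials, as stated.

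**Step 2: chance that one arm's paired test is significant.** p(d) = P(|T| > t at 0.975 with 9 df), where T is noncentral t with noncentrality d√10.

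**Step 3: chance of the misleading patterns when all arms lose the same amount**
- One given arm significant, another given arm not: p(1 − p).
- Control significant, at least one of the two treated arms not: p(1 − p²).

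| d | p | p(1 − p) | p(1 − p²) |
|---|---|---|---|
| 0 | 5.0% | 4.8% | 5.0% |
| 0.3 | 13.6% | 11.8% | 13.4% |
| 0.5 | 29.3% | 20.7% | 26.8% |
| 0.7 | 50.6% | 25.0% | 37.7% |
| 0.8 | 61.6% | 23.6% | 38.2% |
| 1.0 | 80.3% | 15.8% | 28.5% |
| 1.2 | 92.0% | 7.3% | 14.1% |
| 1.5 | 98.7% | 1.3% | 2.5% |
| 2.0 | about 100% | about 0% | about 0% |

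Example at d = 0.5: 0.293 × (1 − 0.293²) = 0.293 × 0.914 = 0.268. The last column peaks where 1 − 3p² = 0, that is p = 1/√3 = 0.577 (d about 0.76), with value 0.577 × 2/3 = 0.385.

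**Step 4: direct comparison of change between arms, same scenario.** In 40,000 simulated trials at each of four values of d from 0.5 to 1.0, one-way ANOVA on the changes was significant in 4.9% to 5.1%. Tukey declared a difference between control and either treated arm in 3.6% to 3.7%.

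**Step 5: the opposite error.** Suppose control loses 2.0 SD and treatment halves this to 1.0 SD. The treated arm's own paired test is still significant in 80.3% of trials (table, d = 1.0).

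**The case against.** The strongest reply is that the SAP already plans between-arm tests and lists them before the paired test. Neither document says that preservation will be concluded from differing within-arm P values. The single threshold is a general convention, not a decision rule, and asking whether each arm's ridge changed is a fair descriptive question. All of this stands, and it rules out several stronger readings.

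- A reader might infer that the paired test is the trial's whole analysis of ridge dimensions. It is not: ANOVA and Tukey are planned.
- A reader might infer that 13% to 38% is the trial's false-positive rate. It is the frequency of a pattern of P values that no planned test uses. It misleads only if someone draws the treatment conclusion from that pattern.
- A reader might note that the three arms fail to agree in up to 75% of trials. That figure counts discordance in every direction, including patterns that favour control, so it does not measure this error.
- A reader might take the problem to be general. It fades once the common loss reaches about 1.5 SD, where nearly every arm is significant and the paired test simply says nothing about treatment.

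It can also be said that the aim names the contrast of the two atorvastatin arms, not treated against empty sockets. That is correct, but the same flaw applies to any pair of arms, as the p(1 − p) column shows.

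The reply does not close the gap. The between-arm tests have no stated variable, so the plan contains no explicit between-arm test of change, and nothing says which result decides.

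**Conclusion.** The concern holds as a gap in what the SAP specifies, not as an invalid planned inference. The SAP should state that treatment conclusions on height and width come from a between-arm comparison of change, and that within-arm results are descriptive. With the same true loss in all arms, reading treatment effects from within-arm P values would produce the misleading control-versus-treated pattern in about 13% to 38% of trials for losses of 0.3 to 1.2 SD of change, falling to 2.5% at 1.5 SD. ANOVA on change holds its rate at about 5%. These sizes rest on the assumed standardised loss, normal changes, two-sided tests and 10 complete patients per arm. The point is limited to bone height and width, because histomorphometry has no baseline and so no within-arm change to test. It is a worthwhile, inexpensive correction.

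**What to change.** In the SAP:

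1. Replace the paired t tests with the mean baseline-to-8-week change and its 95% CI in each arm, for height and for width, labelled descriptive.
2. Name the between-arm variable. Either apply ANOVA and Tukey to the baseline-to-8-week change, or use ANCOVA of the 8-week value adjusted for baseline. Choose one and report the between-arm differences with 95% CIs.
3. Add a sentence such as: *Conclusions about treatment effects on bone height and width will rest only on the between-arm comparison of change from baseline to 8 weeks; significance or non-significance of the change within an arm will not be used as evidence of preservation.*

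The cost is a few sentences and the loss of the within-arm P values. No extra data or patients are needed. The SAP is written in the past tense, but the same rule can still govern how the results are reported.
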